8.6 Off Study Criteria

8.6.1 Per Patient choice: Patients may withdraw from study at their request. The risks of withdrawing will be discussed, as will alternative treatment options. Those subjects who choose to withdraw while taking Eltrombopag will be strongly encouraged to continue to have labs monitored until he/she initiates alternative therapy.

8.6.2 Per principal investigator decision: Should any of the following adverse events occur during the 16 week study period, or in the extension treatment arm in responders, eltrombopag will be discontinued. The subject will be followed until resolution of the event. Labs will be monitored through 30 days off study drug time point or until he/she initiates alternative disease directed therapy at which time the subject's participation on this study will be considered complete and the subject will go off study.

- Intolerance of eltrombopag not resolved by dose reduction
- Life threatening acute hypersensitivity reaction
- Thrombosis/embolism (DVT, PE, stroke or TIA, myocardial infarction) other than central line thrombosis
- Persistent hepatotoxicity as defined in section 5.3.2
- New or worsening morphological abnormalities or cytopenia(s) as defined in section 5.4.2

- No treatment response after 16 to 20 weeks of treatment
- Any Grade IV toxicity considered related to the study medication excluding readily reversible metabolic or laboratory abnormalities or hematologic toxicities
- Significant progression of disease or a concomitant condition that would make the subject ineligible for further protocol participation
- Pregnancy or unwillingness to use acceptable forms of contraception
- Initiation of non-protocol therapy for aplastic anemia or bone marrow failure and unilineage cytopenia
- Cytogenetic abnormalities, new or worsening morphological abnormalities or cytopenia(s) as defined in section 5.4.2.
- Non-compliance with protocol procedures
- Lost to follow-up
- Study Completion

Once off study (either by per patient choice or per PI decision), subjects will be referred back to his or her referring physician or consented to the Hematology Branch evaluation and treatment protocol (94-H-0010) for consideration for standard therapy or evaluation for eligibility for another Branch protocol, depending on what is considered to be in the best interest of the subject.

9 DATA AND SAFETY MONITORING

9.1 Data and Safety Monitoring

Principal Investigator: Accrual, efficacy and safety data will be monitored by the Principal Investigator, [name].

NIH Intramural IRB. Accrual and safety data will be monitored and reviewed annually by the Institutional Review Board (IRB). Prior to implementation of this study, the protocol and the proposed patient consent and assent forms will be reviewed and approved by the properly constituted Institutional Review Board (IRB) operating according to Title 45 CFR 46. This committee will also approve all amendments to the protocol or informed consent, and conduct continuing annual review so long as the protocol is open to accrual or follow up of subjects.

NHLBI DSMB: The NHLBI Data safety and Monitoring Board will review the protocol at 6 to 12 month intervals. A progress report will be forwarded to the DSMB at these times and their recommendations will be expeditiously implemented. The DSMB may recommend early termination of the study for considerations of safety and efficacy.

Monitoring: As per ICH-GCP 5.18 and 21 CFR 312.50, clinical protocols are required to be adequately monitored by the study sponsor. The monitoring of this study will be conducted by Clinical Research Associates (CRAs)/Monitors employed by an independent contract organization working under an agreement with NHLBI to monitor aspects of the study in accordance with the appropriate regulations and the approved protocol. The objectives of a monitoring visit will be: 1) to verify the existence of signed informed consent form (ICF) and documentation of the ICF process for each monitored subject; 2) to verify the prompt and accurate recording of all monitored data points, and prompt reporting of all SAEs; 3) to compare abstracted information with individual subjects' records and source documents (subject's charts, laboratory analyses and test results, physicians' progress notes, nurses' notes, and any other relevant original subject information); and 4) to help ensure investigators are in compliance with the protocol. The monitors also will inspect the clinical site regulatory files to ensure that regulatory requirements (Office for Human Research Protections-OHRP) and applicable guidelines (ICH-GCP) are

being followed. During the monitoring visits, the investigator (and/or designee) and other study personnel will be available to discuss the study progress and monitoring visit.

The investigator (and/or designee) will make study documents (e.g., consent forms and pertinent hospital or clinical records readily available for inspection by the local IRB, the site monitors, and the NHLBI staff for confirmation of the study data.

FDA: Under IND 104,877 an annual progress report, any amendments to the protocol, and any change in the status of the protocol will be forwarded to FDA to via the Project Manager or designee:

Novartis: An annual progress report, any amendments to the protocol, and any change in the status of the protocol will be forwarded to the CRADA Sponsor.

9.2 Event Characterization and Reporting

Events include adverse events (AE), serious adverse events (SAE), protocol deviations (PD), unanticipated problems (UP), and non-compliance.

The principal investigator will review all events (AEs, protocol deviations, UPs, SAEs) to determine the seriousness, expectedness, and reportability of the event. As required and/or needed, the principal investigator will review the events with the Sponsor to make the final determination of seriousness and reportability.

9.2.1 Definitions

Adverse Event (AE): Any untoward or unfavorable medical occurrence in a human subject, including any abnormal sign (e.g., abnormal physical exam or laboratory finding), symptom, or disease, temporally associated with the subject's participation in the research, whether or not considered related to the research.

Serious Adverse Event (SAE): A serious adverse event that:

- results in death;
- is life-threatening (places the subject at immediate risk of death from the event as it occurred);
- results in in-patient hospitalization or prolongation of existing hospitalization;
- results in a persistent or significant incapacity;
- results in a congenital anomaly/birth defect; or
- based upon appropriate medical judgment, may jeopardize the subject's health and may require medical or surgical intervention to prevent one of the other outcomes listed in this definition.

Suspected adverse reaction: Suspected adverse reaction means any adverse event for which there is a reasonable possibility that the drug caused the adverse event. For the purposes of IND safety reporting, 'reasonable possibility' means there is evidence to suggest a causal relationship between the drug and the adverse event. A suspected adverse reaction implies a lesser degree of certainty about causality than adverse reaction, which means any adverse event caused by a drug.

Serious event: An event is serious if it meets the definition of a serious adverse event (above) or if it requires immediate corrective action by a PI and/or IRB to protect the safety, welfare or rights of subjects.

Unexpected adverse reaction: An adverse event or suspected adverse reaction is considered "unexpected" if it is not listed in the investigator brochure or is not listed at the specificity or severity that has been observed; or, if an investigator brochure is not required or available, is not consistent with the risk information described in the general investigational plan or elsewhere in the current application. "Unexpected", also refers to adverse events or suspected adverse reactions that are mentioned in the investigator brochure as occurring with a class of drugs or as anticipated from the pharmacological properties of the drug, but are not specifically mentioned as occurring with the particular drug under investigation.

Unanticipated Problem (UP): Any incident, experience, or outcome that meets all of the following criteria:

1. unexpected in terms of nature, severity, or frequency in relation to
 - a. the research risks that are described in the IRB-approved research protocol and informed consent document; Investigator's Brochure or other study documents; and
 - b. the characteristics of the subject population being studied; and
2. related or possibly related to participation in the research; and
3. places subjects or others at a greater risk of harm (including physical, psychological, economic, or social harm) than was previously known or recognized.

Unanticipated Problem that is not an Adverse Event: An unanticipated problem that does not fit the definition of an adverse event, but which may, in the opinion of the investigator, involves risk to the subject, affect others in the research study, or significantly impact the integrity of research data. For example, report occurrences of breaches of confidentiality, accidental destruction of study records, or unaccounted-for study drug.

Protocol Deviation (PD): Any change, divergence, or departure from the IRB approved research protocol.

Eltrombopag dose may be interrupted when clinically indicated at the discretion of the investigator. These interruptions will not be reported as deviations; however, when the interruption is a consequence to a serious adverse event, the interruption will be included in the SAE NIH Problem Report.

Interruptions such as delays in request for medication refills or medication errors by subjects, unless they

result in a serious adverse event or impact the integrity of the research data, will not be reported as deviations to the IRB, but will be recorded in the medical record.

Non-compliance: The failure to comply with applicable NIH HRPP policies, IRB requirements, or regulatory requirements for the protection of human research. Noncompliance may be further characterized as:

1. **Serious non-compliance:** Non-compliance that:

- a. Increases risks, or causes harm, to participants.
- b. Decreases potential benefits to participants.
- c. Compromises the integrity of the NIH HRPP.
- d. Invalidates the study data.

2. **Continuing non-compliance:** Non-compliance that is recurring. An example may be a pattern of non-compliance that suggests a likelihood that, absent an intervention, non-compliance will continue. Continuing noncompliance could also include a failure to respond to IRB requests to resolve previous allegations of non-compliance.

3. **Minor (non-serious) non-compliance:** Non-compliance that, is neither serious nor continuing.

9.2.2 Adverse Events Management:

All adverse events occurring during the study, including those observed by or reported to the research team, will be recorded. The AEs will be attributed (unrelated, unlikely, possibly, probably or definitely) to study medication and/or disease and graded by severity utilizing CTC version 4.0. A copy of the criteria can be down-loaded from the CTEP home page at <http://ctep.cancer.gov/reporting/ctc.html>.

Eltrombopag has known and unknown toxicity profiles, thus, any observed or volunteered adverse events that are as listed in the Package Insert and/or Investigator's Brochure will not be reported unless (1) the adverse event was not present at baseline exam; (2) the adverse event is previously unknown (not on the label); (3) the adverse event is more severe than on the label; (4) the frequency of the adverse events increases above the listed frequency; or (5) meets the criteria for a serious adverse event.

Abnormal laboratory findings used to evaluate the safety of this protocol regimen will be collected to include any change from laboratory assessments done prior to first dose of study medication that result in a progression to a grade 3 or 4 laboratory toxicity and/or are characterized by any of the following:

- Results in discontinuation from the study
- Is associated with clinical signs or symptoms
- Requires treatment or any other therapeutic intervention
- Is associated with death or another serious adverse event, including hospitalization
- Is judged by the Investigator to be of significant clinical impact
- If any abnormal laboratory result is considered clinically significant, the investigator will provide details about the action taken with respect to the test drug and about the patient's outcome.

In view of the underlying illness, bone marrow failure, all patients will enter the study with abnormally low blood counts that would meet criteria as grade 3 or more commonly grade 4 toxicity, and requiring frequent platelet and/or red cell transfusions, and thus AEs regarding hematologic lab values including thrombocytopenia or platelet-transfusion dependence, anemia or red cell transfusion dependence, neutropenia, lymphopenia, or leukopenia will not be evaluable. Thus, we will collect hematologic laboratory values in the subject's source documents, but will not record or report these as adverse events.

Abnormal laboratory values recorded in the database will be recorded at the highest grade and resolved in the database when the value is a grade 2 or lower.

Hypertension CTCAEv4 Grade 1 is not an applicable category for this study and therefore only hypertension greater than grade 2, that require medical intervention, will be documented.

Unscheduled laboratory results or patient reports that have been sent in addition to the protocol required ones will be reviewed for AE's and if not qualifying for an AE Grade 3 or 4 will be recorded in CRIS but not in the studies database. Grade 3 or 4 AE qualifying information will be reported in the database.

The laboratory toxicities will be attributed (unrelated, unlikely, possibly, probably or definitely) to study medication and/or disease and graded by severity utilizing CTC version 4.0.

Duration of adverse event collecting and reporting: Thirty days after the last dose of study drug, adverse event reporting will be limited to those events considered possibly, probably, or definitely related to study drug.

Grading of Adverse events:

1	Mild	Symptom barely noticeable to subject; does not influence performance or functioning. Prescription drug not ordinarily needed for relief of symptom but may be given because of personality of subject.
2	Moderate	Symptom of a sufficient severity to make subject uncomfortable; performance of daily activities influenced; subject is able to continue in study; treatment for symptom may be needed.
3	Severe	Symptom causes severe discomfort. May be of such severity that subject cannot continue. Severity may cause cessation of treatment with test drug; treatment for symptom may be given and/or subject hospitalized.
4	Life-threatening	Symptom(s) place the patient at immediate risk of death from the reaction as it occurred; it does not include a reaction that, had it occurred in a more serious form, might have caused death.

Attribution of Adverse Events:

Criteria for Determining Category of Relationship of Clinical Adverse Events to Treatment		
1	Not related	This category applies to those adverse events which, after careful consideration, are clearly and incontrovertibly due to extraneous causes (disease, environment, etc.)
2	Unlikely (must have two)	In general, this category can be considered applicable to those adverse events which, after careful medical consideration at the time they are evaluated, are judged to be unrelated to the test drug. An adverse event may be considered unlikely if or when: 
 1. It does not follow a reasonable temporal sequence from administration of the test drug. 2. It could readily have been produced by the subject's clinical state, environmental or toxic factors, or other modes of therapy administered to the subject. 3. It does not follow a known pattern of response to the test drug. 4. It does not reappear or worsen when the drug is re-administered.
3	Possibly (must have two)	This category applies to those adverse events for which, after careful medical consideration at the time they are evaluated, a connection with the test drug administration appears unlikely but cannot be ruled out with certainty. An adverse event may be considered possibly related if or when: 
 1. It follows a reasonable temporal sequence from administration of the test drug. 2. It could not readily have been produced by the subject's clinical state, environmental or toxic factors, or other modes of therapy administered to the subject. 3. It follows a known pattern of response to the test drug.

4	Probably (must have three)	
This category applies to those adverse events for which, after careful medical consideration at the time they are evaluated, are felt with a high degree of certainty to be related to the test drug. An adverse event may be considered probably related if or when:
 
 1. It follows a reasonable temporal sequence from administration of the test drug. 2. It could not be reasonably explained by the known characteristics of the subject's clinical state, environmental or toxic factors, or other modes of therapy administered to the subject. 3. It disappears or decreases on cessation or reduction in dose. There are important exceptions when an adverse event does not disappear upon discontinuation of the drug, yet drug-relatedness clearly exists (e.g., bone marrow depression, fixed drug eruptions, tardive dyskinesia). 4. It follows a known pattern of response to the test drug.
5	Definitely (must have all)	
This category applies to those adverse events which, the Investigator feels are incontrovertibly related to test drug. An adverse event may be assigned an attribution of definitely related if or when:
 
 1. It follows a reasonable temporal sequence from administration of the test drug. 2. It could not be reasonably explained by the known characteristics of the subject's clinical state, environmental or toxic factors, or other modes of therapy administered to the subject. 3. It disappears or decreases on cessation or reduction in dose with re-exposure to drug. (Note: this is not to be construed as requiring re-exposure of the subject, however, a category of definitely related can only be used when a recurrence is observed.) 4. It follows a known pattern of response to the test drug.

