Patients will be enrolled on study because of anemia and/or thrombocytopenia. The majority of patients are expected to have cytopenias in both lineages, however some patients will have normal or close to normal counts in one or the other lineage at baseline. Therefore, dose escalation criteria will vary depending on whether one or both lineages meet inclusion criteria. Escalation will occur via the tables below and continue to the maximum dose until the inclusion criterion lineage or lineages responds, according to the schema set out below, unless toxicity-related stopping or dose reduction lab values occur. Note that patients entering the study based on anemia, with normal or near normal platelet count, will be expected to have an increased in their platelet count on eltrombopag, but dose escalation for anemia will not be halted unless the platelet count goes above 400,000/uL. For patients entering meeting both anemia and thrombocytopenia eligibility criteria, dose escalation will not stop until both lineages reach the thresholds given below to stay on the current dose, unless platelets go over 400,000/uL or hemoglobin goes over 16.0 gr/dL, in which case drug will be discontinued for one week and the dose decreased by 50%.

Dose Escalation for Patients Entering with Platelets <30,000/uL or transfusion-dependence:

Platelet Count < 30,000/uL or transfusion-dependent at baseline	Dose Adjustment or Response
<20,000/uL above baseline	Increase daily dose by 50 mg (25 mg for East Asians) every 4 weeks to maximum 300 mg/day for non- East Asians (150 mg/day for East Asians).
≥20,000/uL above baseline but ≤200,000/uL following at least 2 weeks of eltrombopag	Keep at current dosage.
>200,000/uL (untransfused) at any time on	Decrease dosage by 50 mg (25

Platelet Count < 30,000/uL or transfusion-dependent at baseline	Dose Adjustment or Response
study	mg for East Asians) every 4 weeks to lowest dosage that maintains platelet count $\geq 20,000/uL$ above baseline.
>400,000/uL (untransfused) at any time on study	Discontinue eltrombopag for one week, if platelets < 20,000/uL; restart at 50% of current dose.

Dose Escalation for Patients Entering with Anemia (Hb < 8.5gr/dL or transfusion-dependence)

Hemoglobin < 8.5 gr/dL or transfusion dependent at baseline	Dose Adjustment or Response
Hemoglobin rise of < 1.5 g/dL.	Increase daily dose by 50 mg (25 mg for East Asians) every 4 weeks to maximum 300mg/day for non- East Asians (150mg/day for East Asians).

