8.2 Endpoints

The **primary endpoint** will be the portion of drug responders as defined by changes in the platelet count and/or platelet transfusion requirements or hemoglobin and/or PRBC transfusion requirements and the toxicity profile as measured using the CTCAE criteria. Treatment response for the platelet lineage is defined as an absolute increase of $\geq 20 \times 10^9/L$ above baseline at 16 or 20 weeks, measured on at least two serial measurements performed one week apart and sustained for 1 month or more without support of platelet transfusions, or for transfusion dependent patients stable platelet counts with transfusion independence for ≥ 8 weeks. For patients with anemia (untransfused hemoglobin ≤ 8.5 g/dL), a treatment response will be an increase in Hb by ≥ 1.5 g/dL at four months, measured on at least 2 serial measurements and sustained for 1 month or more without transfusion support **OR** for transfusion dependent patients, reduction of units of RCC transfused by 50%/8 weeks compared with the pretreatment transfusion number in the previous 8 weeks or transfusion independence (no transfusions for ≥ 8 weeks).

Criteria for response: Treatment response for the platelet lineage is defined as platelet count increases to 20,000/uL above baseline at 16 or 20 weeks, or freedom from platelet transfusions for ≥ 8 weeks in transfusion-dependent patients. For patients with anemia (untransfused hemoglobin ≤ 8.5 g/dL), a treatment response will be an increase in Hb by ≥ 1.5 g/dL at four months, measured on at least 2 serial measurements and sustained for 1 month or more without transfusion support **OR** for transfusion dependent patients, reduction of units of RCC transfused by 50%/8 weeks compared with the pretreatment transfusion number in the previous 8 weeks or transfusion independence (no transfusions for ≥ 8 weeks). We will analyze a composite of both lineage responses and the individual responses.

Secondary endpoints will include incidence of bleeding, changes in serum thrombopoietin level (as measured by enzyme-linked immunosorbent assay), clonal evolution to PNH, clonal chromosomal population in bone marrow, myelodysplasia by morphology, or acute leukemia and health related *General Quality of Life (FACT questionnaire)* for Subjects ages 18 and older will be completed at baseline and 16 weeks.

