8.5 Stopping rules

The study will be monitored to ensure that the occurrence of a specified set of treatment related serious adverse events (TRSAEs) that occur during the treatment period does not substantially exceed an anticipated rate. The following specified TRSAEs determined to be probably or definitely related to eltrombopag will be considered for early stopping of the study:

1. Death
2. Any Grade IV toxicity excluding readily reversible metabolic or laboratory abnormalities
3. Grade IV thrombosis/embolism

We anticipate the rate of these specified TRSAEs within the 3 month study period to be 20% or less. Following Geller et al. (12), our stopping rule is determined by a Bayesian approach. The stopping boundary for an experiment is reached if the Bayesian posterior probability that the true probability of developing one or more of the specified TRSAE's exceeds this benchmark rate of 20% is at least 90%. We take our prior distribution to be a beta distribution with parameters $(\alpha, \beta) = (0.72, 2.88)$, so that $\alpha + \beta = 3.6$ is approximately 15% of the expected sample size. The parameter are chosen so that the mean $\alpha / (\alpha + \beta) = 0.2$ as the expected proportion of specified TRSAE's and the sum $\alpha + \beta = 3.6$ as the "worth" we place on our prior clinical opinion. Practical interpretations and justifications of the Bayesian approach and the choice of the prior distributions can be found in Geller et al. Since we have seen in the past that the first few subjects to be accrued are possibly sicker than the rest of the subjects in the sample, we will start safety monitoring when 3 or more subjects have developed a TRSAE. The following table summarizes the threshold numbers for stopping the study.

Number of subjects in the experiment	Stop if the number of subjects who have developed any of the specified TRSAE's reaches:
≤ 5	3
≤ 9	4
≤ 13	5
≤ 16	6
≤ 20	7
≤ 24	8
≤ 28	9
≤ 33	10

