9.2.3 Serious Adverse Events Management

Serious adverse events will be attributed as definitely (clearly related to the research), probably (likely related to the research), possibly (may be related to the research), unlikely (doubtfully related to the research) and unrelated (clearly not related to the research).

Treatment related SAEs (TRSAEs) are those attributed as definitely, probably, or possibly related that will be monitored and considered for early stopping of the study according to statistically determined criteria. These include death and any grade IV toxicity considered to be probably or definitely related to study medication. [name] will serve as the independent monitor who reviews the attribution of TRSAEs.

Hospitalizations for administrative issues (to receive a transfusion) or upgrading to ICU for routine monitoring will not be reported as an SAE.

Duration of Serious Adverse Event collecting and reporting: The collection of SAEs will begin on the first day of initiation of the study drug and will continue along as the subject is on study.

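### Section 9.2.2 bars all low counts from adverse event recording because every patient is said to enter at grade 3–4, yet some lineages are intact at entry, and the sections disagree on whether a grade IV cytopenia counts for the stopping rule

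*Combined protocol and SAP*

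**What the plan says.** - **Exclusion (9.2.2).** Low platelets, anemia, neutropenia, lymphopenia, leukopenia and transfusion dependence are declared not evaluable as adverse events. Values are kept in source documents, but the team "will not record or report these as adverse events".
- **Reason given (9.2.2).** "all patients will enter the study with abnormally low blood counts that would meet criteria as grade 3 or more commonly grade 4 toxicity", together with frequent transfusion need.
- **General laboratory rule (9.2.2, immediately before).** Changes from pre-dose values that "result in a progression to a grade 3 or 4 laboratory toxicity" are collected.
- **Baseline status (5.2).** "some patients will have normal or close to normal counts in one or the other lineage at baseline". The same paragraph speaks of "patients entering the study based on anemia, with normal or near normal platelet count".
- **Primary endpoint (8.2).** Response, plus "the toxicity profile as measured using the CTCAE criteria".
- **Stopping rule (8.5, item 2).** "Any Grade IV toxicity excluding readily reversible metabolic or laboratory abnormalities", when probably or definitely related.
- **Treatment-related SAEs (9.2.3).** "These include death and any grade IV toxicity considered to be probably or definitely related to study medication".
- **Off-study criteria (8.6.2).** The item on related grade IV toxicity leaves out hematologic toxicities. Two other items in the same list, which is introduced as a list of adverse events, name new or worsening cytopenias as defined in 5.4.2.

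**The concern.** A lineage already at grade 3 or 4 cannot show a new grade 3 or 4 event, so setting it aside is reasonable. The exclusion goes further: it applies to every lineage of every patient, on a premise about patients that the protocol itself contradicts for individual lineages.

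Two things are at stake. The first is half of the primary endpoint. A CTCAE toxicity profile built from adverse event entries would show no laboratory cytopenias whatever happened, including in patients whose platelets or neutrophils were normal at entry. The second is the safety boundary. Grading and attribution are defined for recorded events, so it is unclear how an event barred from recording would reach the count in Section 8.5.

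**Working it through.** **Step 1. Test the premise against eligibility (4.1.1, 4.2).**

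| Entry route | Lineages that must be low | Lineages that need not be low |
|---|---|---|
| Moderate aplastic anemia | at least 2 of 3 | up to 1 |
| Unilineage failure | 1 (red cell or platelet) | up to 2 |

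Neither route requires transfusion dependence. For example, a qualifying neutrophil count with a qualifying platelet count is enough for the first route. Counts meeting severe criteria are excluded (4.2.2). Section 5.2 confirms that patients with an intact lineage are expected. The premise may hold for a patient's affected lineage but does not hold for all lineages. The protocol prints no CTCAE cut-offs, so this step rests on the normal or near-normal counts in 5.2, not on grading the eligibility limits.

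**Step 2. Follow one event through the plan.** Take an anemia entrant with normal platelets whose platelets fall to grade 4 on drug.

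- The general rule in 9.2.2 would collect it, as progression from pre-dose values.
- The next paragraph of 9.2.2 says not to record it as an adverse event.
- Section 5.4.2 acts on worsening anemia or neutropenia and does not name platelets.
- Section 9.2.3 also leaves out of SAE reporting an admission made to receive a transfusion.

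The number of graded, attributed entries is therefore zero by rule. Elsewhere the protocol treats such events as possible and reportable. The attribution table in 9.2.2 uses bone marrow depression as an example of a drug-related event, and the expected-event list for severe aplastic anemia in 10.3.1 includes anemia.

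**Step 3. Compare the sections on a related grade IV cytopenia.**

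| Section | Treatment |
|---|---|
| 8.5 item 2 | Counts unless readily reversible; no hematologic exclusion |
| 9.2.3 | Counts; no hematologic exclusion |
| 8.6.2, grade IV item | Hematologic toxicity excluded |
| 8.6.2, cytopenia items | Worsening cytopenia per 5.4.2 is called an adverse event |
| 9.2.2 | Not recorded as an adverse event |

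These cannot all be followed for the same event.

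**Step 4. Sensitivity of the boundary.** First, the plan's own figures. Inputs from 8.5: prior Beta(0.72, 2.88), benchmark 20%, posterior threshold 90%, 33 subjects, no stop before 3 events. The boundary is the smallest k ≥ 3 with P(p > 0.20 | k, n) ≥ 0.90 under Beta(0.72 + k, 2.88 + n − k). This gives the printed boundary at every n from 3 to 33 except n = 33, where 10 events give 0.8994. An exact sequential binomial recursion with the printed boundary gives:

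| True p | 0.10 | 0.20 | 0.25 | 0.30 | 0.40 |
|---|---|---|---|---|---|
| Plan (simulation) | 1.8% | 22.4% | 43.9% | 66.7% | 93.9% |
| Exact | 1.9% | 22.3% | 43.9% | 66.6% | 93.9% |

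The stopping probabilities are reproduced.

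Now suppose that a share h of subjects has a qualifying event only through an uncounted cytopenia, so the boundary sees p − h. The documents give no value for h, so the range below is an assumption:

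| True p | h = 0 | h = 0.05 | h = 0.10 | h = 0.15 |
|---|---|---|---|---|
| 0.25 | 43.9% | 22.3% | 8.1% | 1.9% |
| 0.30 | 66.6% | 43.9% | 22.3% | 8.1% |
| 0.40 | 93.9% | 84.0% | 66.6% | 43.9% |

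This shows what follows if 9.2.2 governs the count. It does not show that 9.2.2 does govern it.

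**The case against.** A reader might infer that new cytopenias vanish from the trial and can never count toward the stopping boundary. The documents do not support that.

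- **Stopping rule.** Sections 8.5 and 9.2.3, read alone, count a related grade IV cytopenia that is not readily reversible. Section 8.6.2 shows that the authors could write a hematologic exclusion, and 8.5 has none. What can be shown is a contradiction.
- **Worsening cytopenia.** The protocol is not silent: 8.6.2 calls it an adverse event that ends treatment, and one trigger in the 9.2.2 laboratory rule is a finding that leads to discontinuation from the study.
- **Data.** Blood counts are taken at least every two weeks on drug, and Sections 6.2 and 6.3 say all laboratory data will be recorded. They are also the efficacy measurements. Shifts from baseline can be tabulated whatever the event coding.
- **Scope.** Every item that 9.2.2 lists is a low count or a transfusion need. Thrombocytosis and erythrocytosis are not listed. Death and thrombosis remain stopping events, bleeding and clonal evolution are secondary endpoints, and infection remains reportable.
- **Practical effect.** Probable attribution needs three of four criteria, and marrow failure makes it hard to say that the clinical state does not explain the event. A cytopenia that resolves quickly may count as readily reversible. Few events may reach the boundary under any reading.

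All of this stands, and it limits the point. It does not restore graded, attributed cytopenias to the adverse event data behind the toxicity endpoint, and it does not settle which section governs.

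**Conclusion.** The exclusion in 9.2.2 is wrong as written and should be corrected. Its premise fails for any lineage intact at entry, and in those lineages the rule yields no adverse event entries for new grade 3 or 4 cytopenias. The loss is confined to event coding: the counts survive and clinical consequences are still captured.

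For the stopping rule, the finding is an unresolved conflict between 8.5, 8.6.2, 9.2.2 and 9.2.3. The drops in stopping probability in step 4 apply only if 9.2.2 prevails, and only for the assumed values of h.

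The number of subjects with an intact lineage is not given; Section 5.2 says only that most are expected to be low in both the red cell and platelet lineages. The number of events is not given either. The problem is worth correcting but does not by itself invalidate the design.

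**What to change.** 1. In 9.2.2, limit the exclusion to lineages already at grade 3–4 or transfusion-dependent at baseline, and record baseline grade by lineage.
2. For every other lineage, apply the rule 9.2.2 already uses for laboratory findings: record progression from pre-dose values to grade 3 or 4, with attribution.
3. Add a table of count shifts from baseline by lineage to the planned analyses.
4. Reconcile 8.5, 8.6.2, 9.2.2 and 9.2.3 so that they give one answer on whether hematologic grade IV toxicity counts as a treatment-related SAE for the boundary.

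The cost is a short text change in 9.2.2, matching wording in the other three sections, and a few more adverse event entries. No extra blood draws are needed, and because source counts are kept, the rule can be applied to subjects already enrolled. Some added entries, mainly in mildly depressed lineages, will be hard to separate from the underlying disease in a single-arm trial. The shift table should be read with that in mind.
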